14.2 CARDIAC EVENTS

In a safety analysis of two Phase 3 trials of Maraviroc involving 840 HIV-infected subjects who received at least one dose of Maraviroc over 34 weeks, including 426 who received twice daily dosing, 1.3% of subjects had cardiovascular events. More subjects in the Maraviroc group experienced cardiovascular events than in the placebo group, but the link to the drug was unclear and symptoms occurred only in those with known cardiac disease. Given that our population may higher baseline risk of cardiac events, subjects with Acute Coronary Syndrome (ACS) within 6 months of enrollment will be excluded. In addition, participants will be monitored for symptoms of cardiac ischemia, heart failure or arrythmia with further investigation driven inpatient care team. The study team does not plan to routinely check cardiac biomarkers in asymptomatic patients. The safety monitor may request trial stoppage if a grade 3 or 4 adverse cardiac event occurs in any trial participant reasonably attributable to Maraviroc.

Maraviroc does not affect the QT interval.

Given the high incidence of hepatitis at baseline in SARS-CoV-2 patients, we expect to observe high incidence of low-grade liver function test abnormalities during lab monitoring. Therefore, we elect to implement Common Terminology Criteria for Adverse Events (CTCAE) v5.0, which incorporates change in liver function testing from baseline to characterize AE grade. The recommendation from the FDA labeling is to obtain liver function tests prior to starting the drug and again should symptoms such as rash occur. We will obtain both baseline and repeat liver function test should allergic symptoms such as rash occur. Liver function testing obtained per routine care will be collected daily. Exposure adjusted rates of Grade 3 or 4 changes in liver function testing resulting in discontinuation will be calculated at the point in which eight patients have received more than four doses of treatment. The Medical Monitor may request trial stoppage in the instance that an unacceptable rate of Grade 3 or 4 changes in liver function testing resulting in discontinuation reasonably attributable to Maraviroc is observed.

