	 activities OR hospitalized pending disposition, not requiring COVID-related care; 3, hospitalized, not requiring supplemental oxygen; 4, hospitalized, requiring supplemental oxygen; 5, hospitalized, requiring nasal high-flow oxygen therapy, noninvasive mechanical ventilation, or both; 6, hospitalized, requiring ECMO, invasive mechanical ventilation, or both; and, 7, death. Change in biomarker levels (CCL5, IL-6, Chi311, etc) from time of enrollment to completion of therapy or live discharge from the hospital (whichever comes first) 7-, 14- and 28-day all-cause-mortality 	
	Days on mechanical ventilation	
SAFETY EVALUATIONS	Daily, multi-disciplinary safety monitoring with interim analysis after 8 subjects have received four or more doses of Maraviroc.	
PLANNED INTERIM ANALYSES	Exposure-adjusted rates of adverse events and those resulting in discontinuation will be calculated at the point in which 8 patients have received more than four doses of treatment. Serious adverse events will be monitored by the study team on an ongoing basis throughout the study.	
STATISTICS Analysis Plan	 Rates of adverse events by severity and rate of completion of therapy. Change in biomarkers compared to clinical improvement Percent of study population reaching clinical improvement at Day 7 will be compared to published results from Remdesivir for 5 or 10 Days in Patients with Severe COVID-19, and other available clinical trials including The Randomized Evaluation of COVID-19 therapy (RECOVERY) Trial. 	

Version #: 2.8 Version Date: 11/6/2020 Page 4 of 30

TABLE OF CONTENTS

1	BACKGROUND7		7
2	STUDY RATIONALE9		
3 STUDY OBJECTIVES			10
	3.1	Primary Objective	10
	3.2	Secondary Objectives	10
4	STUI	DY DESIGN	10
	4.1	Study Overview	10
5	CRIT	TERIA FOR EVALUATION	10
	5.1	Primary Efficacy Endpoint	10
	5.2	Secondary Efficacy Endpoints	10
6	SUB	JECT SELECTION	11
	6.1	Study Population	11
	6.2	Inclusion Criteria.	11
	6.3	Exclusion Criteria	11
7	CON	CURRENT MEDICATIONS	11
	7.1	Allowed	11
	7.2	Prohibited	12
8	STUI	DY TREATMENTS	12
	8.1	Method of Assigning Subjects to Treatment Groups	12
	8.2	Formulation of Test Product	12
	8.3	Supply of Study Medication at the Site	12
	8.4	Study Medication Accountability	13
	8.5	Measures of Treatment Compliance	14
9	STUI	DY PROCEDURES AND GUIDELINES	14
	9.1	Clinical Assessments	14
	9.2	Clinical Laboratory Measurements	15
	9.3	Research Laboratory Measurements	15
10	EVA	LUATIONS BY VISIT	16
	10.1	Screening/Enrollement (Day 0).	16
	10.2	Visit 1 (Day 1)	16

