12 DISCONTINUATION AND REPLACEMENT OF SUBJECTS

12.1 Early Discontinuation of Study Drug

A subject may be discontinued from study treatment at any time if the subject or the investigator feels that it is not in the subject's best interest to continue. The following is a list of possible reasons for study treatment discontinuation:

- Subject withdrawal of consent (or assent)
- Subject is not compliant with study procedures
- Adverse event that in the opinion of the investigator would be in the best interest of the subject to discontinue study treatment, including stoppage criteria for orthostatic hypotension
- Protocol violation requiring discontinuation of study treatment
- Drug supplier (Pfizer) request for early termination of study, after which study drug cannot be reasonably provided to subjects at no cost to them
- Positive pregnancy test (females)
- Pursuit of comfort measures only, inpatient hospice referral or transfer to inpatient hospice facility

Version #: 2.8 Version Date: 11/6/2020 Page 22 of 30

If a subject is withdrawn from treatment due to an adverse event, the subject will be followed and treated by the study team until the abnormal parameter or symptom has resolved or stabilized.

Subjects who are discharged from the hospital will not continue taking Maraviroc outside the hospital. Early completion prior to seven days of therapy will not be considered early withdrawal from the study. All subjects who discontinue study treatment will undergo an early discontinuation visit as soon as possible and will be encouraged to complete all remaining scheduled research labwork (except in the instance of comfort measures and hospice). Subjects are free to withdraw from participation at any time, for any reason, specified or unspecified, and without prejudice.

Reasonable attempts will be made by the investigator to provide a reason for subject withdrawals. The reason for the subject's withdrawal from the study will be specified in the subject's source documents.

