15.4 Interim Analysis

Refer to Section 14 regarding interim adverse event analysis.

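### The hepatic interim rate in Section 14.3 counts only Grade 3 or 4 liver changes that led to stopping drug, and no liver-specific graded count without that condition is planned at the interim

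*Combined protocol and SAP*

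**What the plan says.** Section 14.3 sets the hepatic interim rate: "Exposure adjusted rates of Grade 3 or 4 changes in liver function testing resulting in discontinuation will be calculated". The timing is "at the point in which eight patients have received more than four doses of treatment". The Medical Monitor may then ask for the trial to stop if an "unacceptable rate of Grade 3 or 4 changes in liver function testing resulting in discontinuation reasonably attributable to Maraviroc is observed". No number is given for what is unacceptable. The same section adopts CTCAE v5.0 for liver tests so that grades reflect change from baseline. It adds that "Liver function testing obtained per routine care will be collected daily", and it commits the study to a baseline test and to a repeat test if allergic symptoms such as rash occur.

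The synopsis, under planned interim analyses, is broader: "Exposure-adjusted rates of adverse events and those resulting in discontinuation will be calculated", at the same eight-patient point. Its statistics entry lists "Rates of adverse events by severity and rate of completion of therapy", with no interim timing. Section 15.4 sends the reader back: "Refer to Section 14 regarding interim adverse event analysis".

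Under Section 12.1, stopping drug for an adverse event is a matter of investigator opinion. The only stoppage criteria it names are for orthostatic hypotension. Drug is not continued after discharge, and "Early completion prior to seven days of therapy will not be considered early withdrawal from the study".

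**The concern.** The numerator depends on a treatment decision as well as on liver injury. Hepatotoxicity is a risk that the protocol itself says carries a boxed warning, yet the one liver-specific rate planned at the interim can be zero while Grade 3 or 4 changes are present. A monitor who reads that rate as the frequency of severe liver change would be reading a different quantity. The stoppage sentence is worded on the same narrow count, so the measure and the review built on it share the gap.

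**Working it through.** The documents give no expected hepatic rate and no threshold, so there is no planned figure to reproduce. The check is of the definition, followed by an illustration of size.

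**Step 1: who falls outside the numerator.**

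| Subject with a Grade 3 or 4 liver change | In the 14.3 rate? | Basis |
|---|---|---|
| Investigator stops drug because of it | Yes | 14.3 |
| Continues on drug | No | 12.1: investigator opinion, no hepatic criterion |
| Drug stops because of discharge | No | 12.1: discharge, not the liver change, ended treatment |
| Change appears after the last dose | No | Nothing is left to discontinue |

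The last row matters because Section 14.3 describes two pre-licensure cases with liver abnormalities 1 to 3 weeks after starting drug, against a 7-day course in Section 4.1. The same section also cites a post-marketing case after four doses, so late onset is not the only pattern.

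**Step 2: comparison with neighbouring sections.** For postural dizziness, Section 14.1 calculates rates, severity and relationship with no discontinuation condition. It applies the condition to orthostatic hypotension. The cardiac trigger in Section 14.2 is a Grade 3 or 4 event reasonably attributable to drug, again with no such condition. The liver restriction is therefore not a general convention of the protocol.

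**Step 3: size.** Let p be the risk of a Grade 3 or 4 liver change and d the share of those changes that leads to discontinuation. Both are assumptions. Over the same exposure, the expected count in n subjects is n × p if all changes are counted and n × p × d as written, so the written rate is d times the Grade 3 or 4 rate. The two agree only when d = 1.

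The chance of at least one counted event is 1 − (1 − p)^n for all changes and 1 − (1 − p × d)^n as written. With n = 8:

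| p | All counted | d = 0.5 | d = 0.25 |
|---|---|---|---|
| 0.10 | 0.570 | 0.337 | 0.183 |
| 0.20 | 0.832 | 0.570 | 0.337 |
| 0.30 | 0.942 | 0.728 | 0.464 |

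For example, with p = 0.20 and d = 0.5: 1 − 0.80^8 = 0.832, against 1 − 0.90^8 = 0.570.

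**Step 4: what one event does to the rate.** Eight subjects with seven days each give 8 × 7 / 365.25 = 0.153 patient-years, so one event is about 652 per 100 patient-years. If each had only five doses (2.5 days, assumed), exposure is 8 × 2.5 / 365.25 = 0.0548 patient-years and one event is about 1,826 per 100 patient-years. Whether a single event is counted therefore moves the rate from zero to somewhere in that range.

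**Step 5: what zero would mean.** No counted event in eight gives a one-sided 95% upper limit of 1 − 0.05^(1/8) = 31% for changes that caused discontinuation. It sets no limit on changes that did not.

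**The case against.** The strongest reply is that the protocol does not rest on this one rate.

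- At the same look, the synopsis already asks for all adverse events and, separately, those leading to discontinuation.
- It also plans rates by severity.
- Section 14.5 lets the monitor request stoppage for a serious event clearly related to drug in any participant, or for a pattern that includes more adverse events. Neither requires discontinuation.
- The 14.3 trigger is discretionary, so the narrow count does not bind the monitor.

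All of this is right, and it limits the point. It does not remove it. The synopsis interim rate is neither liver-specific nor stated to be by grade. An asymptomatic Grade 3 laboratory change need not meet the definition of a serious event in Section 11.2, and Section 11.1 itself separates severe from serious. The Grade 4 provisions in Section 14.5 concern unexpected events, whereas liver toxicity is anticipated in Section 14.3.

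Some stronger readings are tempting, and the documents do not support them:

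- A reader might infer that severe liver changes go unrecorded. They do not: they are captured and graded as adverse events.
- A reader might infer that post-baseline testing is routine care only. Section 14.3 commits to a repeat test if allergic symptoms occur.
- A reader might infer that untested subjects are scored as event-free. No such rule is stated. The fair remark is that they can add exposure without being able to show a laboratory change.
- A reader might infer that a rise on Day 7 cannot lead to discontinuation. Sections 8.1 and 10.9 make Day 7 a dosing day, so this holds only after the last dose.
- A reader might take the early-completion sentence in Section 12.1 as proof that discharged subjects are excluded. It concerns withdrawal from the study. They are outside the rate because discharge ended treatment.

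**Conclusion.** The concern holds for the hepatic interim rate and for the wording of the hepatic stoppage review. Both omit Grade 3 or 4 liver changes that did not cause drug to be stopped, and no liver-specific graded count fills that place at the interim. The rate captures a share d of the Grade 3 or 4 rate. At an assumed 20% risk, the chance of seeing at least one event in eight falls from 83% to 57% with d = 0.5, and to 34% with d = 0.25. These figures assume independent subjects and illustrative values of p and d; the documents supply neither.

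It would go too far to call the 14.3 rate a biased estimate. It is a valid rate of a narrower event, and the problem arises if it stands in for severe liver change as such. Sample size is unaffected. The change should be made, but it is a reconciliation of Section 14.3 with the synopsis and does not show that safety monitoring is absent.

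**What to change.** Reconcile Section 14.3 with the synopsis. At the eight-patient interim and at the end of the study, report the exposure-adjusted rate of all treatment-emergent Grade 3 or higher liver changes (CTCAE v5.0), whether or not drug was stopped, and show those leading to discontinuation as a subset. Give the full count to the Medical Monitor, whose discretion stays as it is; no stopping rule is proposed.

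Keep the exposure-adjusted denominator. State the event window beside it, since changes after the last dose fall outside drug exposure, and state how many subjects had no post-baseline liver test. Do not restrict the main rate to tested subjects: testing is driven by routine care or symptoms, so the restriction would select who is counted.

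Report orthostatic hypotension in Section 14.1 the same way, with all events and discontinuations as a subset.

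The cost is a wording change and one extra table row for each event type, with no new tests. The reported rate may look less favourable. Because contact after discharge is by phone with no scheduled laboratory tests (Section 10.12), the fuller count will still miss changes that nobody tested for, which is why the number untested should be shown.

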14.4 OTHER ADVERSE EVENTS

Additional adverse events commonly reported include fever, cough, rash, abdominal pain, and increased risk of infections including upper respiratory tract infections. Trial data was obtained from patients with HIV infection at greater risk for infection, Immune Reconstitution Syndrome (IRIS), and malignancy which may have been secondary reasons for fever. Acknowledging the anticipated frequency of fever and cough in SARS-CoV-2 patients, the study team will monitor for evidence of secondary infection.

14.5 UNANTICIPATED ADVERSE EVENTS

As the above anticipated adverse events were noted in a population which varies from our study population hospitalized adults with SARS-CoV-2 infection, it is also important to monitor for unexpected adverse events. Serious, un-anticipated adverse events including sepsis, shock, respiratory failure, or death will be closely monitored for and reported. As this is a population with a high risk of adverse outcome related to SARS-CoV-2 itself, course of infection in participants will be monitored for any deviation from the natural history of SARS-CoV-2 infection, based on available clinical trial data and clinical experience. The monitor may request trial stoppage if any unexpected grade 4 event occurs in unacceptable rate due to Maraviroc. They may also request stoppage if there is noted to be a serious adverse event temporally or otherwise clearly related to administration of the drug in any participant, and/or if there is noted to be a pattern of deviation from natural history of SARS-CoV-2 infection towards worsening symptomatology and/or increased incidence of adverse events. The monitor may request trial stoppage if any unexpected grade 4 event probably or definitely attributable to Maraviroc occurs at an unacceptable rate.

15 STATISTICAL METHODS AND CONSIDERATIONS

Prior to the analysis of the final study data, a detailed Statistical Analysis Plan (SAP) will be written describing all analyses that will be performed. The SAP will contain any modifications to the analysis plan described below.

Version #: 2.8 Version Date: 11/6/2020 Page 27 of 30

15.1 Data Sets Analyzed

All eligible subjects who receive at least one dose of the study drug, or who have had more than one set of serum samples available for biomarker testing will be included in the analysis.

15.2 Demographic and Baseline Characteristics

The following demographic variables at screening will be summarized: race, gender, age, height and weight, BMI, hemodialysis, cardiovascular diseases (hypertension, known valvular disease, cardiomyopathies and/or LV systolic or diastolic dysfunction), and pulmonary disease (including OSA, COPD, asthma, interstitial lung disease, cystic fibrosis, bronchiectasis, lung transplant, lung cancer, pulmonary hypertension), oxygen device and requirement at time of enrollment, oxygen saturation on ambient air at time of enrollment, and time from onset of symptoms to presentation to enrollment.

15.3 Analysis of Endpoints

Continuous data obtained will be expressed by mean ± standard deviation (SD) or interquartile range, as applicable. Categorical variables will be reported as frequency and percentages. ICU LOS (and mechanical ventilation LOS, respectively) will be regressed on available laboratory and biomarker data using multivariable linear regression. All analysis will be conducted in a professional statistical program. Mortality and percent of study population reaching clinical improvement at Day 7 will be compared to published results from Remdesivir for 5 or 10 Days in Patients with Severe COVID-19, and other available clinical trials including The Randomized Evaluation of COVID-19 therapy (RECOVERY) Trial.

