Study Protocol:

Open-label study of Maraviroc in Hospitalized Individuals Diagnosed with SARS-CoV-2

NCT04435522

Version Date: 11/6/2020

[name] MD, MS

Clinical Research Protocol

OPEN-LABEL STUDY OF MARAVIROC IN HOSPITALIZED INDIVIDUALS DIAGNOSED WITH SARS-COV-2

Version Date:	11/6//2020
Commercial Product:	Maraviroc
IND Number:	PIND 150411, IND exempt
Development Phase:	Phase 1
Sponsor:	Department of Medicine
Principal Investigator:	Name: [name] MD, MS
	[contact]
	[contact]
	E-mail: [contact]
Medical Monitor:	Name: [name] MD
	[contact]
	E-mail: [contact]

Version #: 2.8 Version Date: 11/6/2020 Page 1 of 30

TITLE	Open-Label Study of Maraviroc in Hospitalized Individuals Diagnosed with SARS-CoV-2
PRINCIPAL INVESTIGATOR	[name] MD, MS
SPONSOR	Department of Internal Medicine
SITE	Rhode Island Hospital The Miriam Hospital
RATIONALE	CCR5 antagonism in SARS-CoV-2 may alter cell trafficking of inflammatory cells, reduce activation of platelets, and may have a role in reversing lymphopenia. Maraviroc may also have anti-viral properties related to binding to SARS-CoV-2 Main Protease beyond its mechanism as a CCR5 antagonist.
STUDY DESIGN	Single-arm, Open-Label, Proof-of-Concept
PRIMARY OBJECTIVE	To establish whether Maraviroc, used at its approved dosage for HIV, is safe and effective in hospitalized patients with SARS-CoV-2.
SECONDARY OBJECTIVES	Investigate the relationship between reduction of inflammatory and other biomarkers (such as IL-6, CCL5, etc.) later in the course of infection and avoidance of respiratory decompensation and death.
NUMBER OF SUBJECTS	16 subjects
SUBJECT SELECTION CRITERIA	 Inclusion Criteria: Male or female ≥ 18 years of age at time of screening Documentation of a SARS-CoV-2 diagnosis as evidenced by positive SARS-CoV-2 PCR within twelve days at time of screening Chest radiography consistent with multi-focal pneumonia or air-space disease Written informed consent obtained from subject and ability for subject to comply with the requirements of the study. Subject able to safely swallow pills or receive Maraviroc through a nasogastric or orogastric tube. Exclusion Criteria: Subjects who are pregnant, breastfeeding, or unwilling to practice birth control during participation in the study. Subjects with the presence of a condition or abnormality that in the opinion of the Investigators would compromise the safety of

Version #: 2.8 Version Date: 11/6/2020 Page 2 of 30

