3.2 Secondary Objectives

The secondary objective is to investigate the relationship between reduction of inflammatory markers (such as IL-6, CCL5, etc.) and clinical outcomes, including avoidance of respiratory decompensation and death.

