5.2 Secondary Endpoints

- Time to clinical improvement, defined as time from enrollment to an improvement of two points on a seven-category ordinal scale (defined below) or live discharge from the hospital, whichever comes first
 - Ordinal scale: 1, not hospitalized with resumption of normal activities; 2, not hospitalized, but unable to resume normal activities OR hospitalized pending disposition, not requiring COVID-related care; 3, hospitalized, not requiring supplemental oxygen; 4, hospitalized, requiring supplemental oxygen; 5, hospitalized, requiring nasal high-flow oxygen therapy, noninvasive ventilation, or both; 6, hospitalized, requiring ECMO, invasive mechanical ventilation, or both; and, 7, death.
- Change in cytokine levels from time of enrollment to completion of therapy or live discharge from the hospital (whichever comes first)
- 7-, 14- and 28-day all-cause-mortality
- Time to improvement to Score of 2 or less (days)
- Days on mechanical ventilation

Version #: 2.8 Version Date: 11/6/2020 Page 10 of 30

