9.3 Research Laboratory Measurements

All samples collected during the study will be labeled with a de-identified, randomly generated specimen ID. Blood samples collected will be shipped overnight to InCell Dx at [name]. InCellDx, a diagnostics company perform PBMC purification upon receiving samples, and will bank specimens to perform analysis on blood samples, including a cytokine panel that will consist of sCD40L, GM-CSF, IFN gamma, IL-2, IL-4, IL-6, IL-8, IL-10, RANTS, TNF-alpha, and VEGF. Using PBMCs, InCellDx will also perform a CCR5 Receptor occupancy analysis. If enough plasma and PBMC samples are banked, banked samples will be sent to the The [name] Lab at the Fred Hutchinson Cancer Center near the end of the study. The [name] Lab will perform additional flow cytometric analysis to provide insight regarding the immune subset distribution and state of activation of the immune system. Additionally, up to three 100 ul alligots of banked plasma will be sent to The [name] Lab at Brown University, who will perform analysis on Chitinase 3-like 1(Chi311) at the end of the study period. Remaining specimen will be stored at InCellDx for up to six months after the end of the study, during which arrangements will be made to return remaining specimen to Lifespan/The Miriam Hospital Infection Diseases And Immunology Center. Remaining specimens will be destroyed 5 years after return to Lifespan. Until that time, these remaining specimens may be used for validation of results or may be used for further research studies.

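### The only biomarker-outcome analysis with a stated method uses ICU and ventilation length of stay with no rule for deaths, so an early or never-ventilated death scores like a rapid recovery

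*Combined protocol and SAP*

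**What the plan says.** The secondary objective (Section 3.2) is to study the "relationship between reduction of inflammatory markers (such as IL-6, CCL5, etc.) and clinical outcomes, including avoidance of respiratory decompensation and death". The synopsis has the same aim and places the biomarker reduction "Investigate the relationship between reduction of inflammatory and other biomarkers (such as IL-6, CCL5, etc.) later in the course of infection".

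The only method offered for this is one sentence in Section 15.3: "ICU LOS (and mechanical ventilation LOS, respectively) will be regressed on available laboratory and biomarker data using multivariable linear regression". It gives no list or maximum number of predictors. It does not choose among the Day 0, 3, 7 and 15/discharge samples, or between level and change. It has no rule for a stay cut short by death or for patients never in ICU or never ventilated.

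The statistics row of the synopsis also lists "Change in biomarkers compared to clinical improvement", without a method. A change window is defined for the biomarker endpoint, "Change in biomarker levels (CCL5, IL-6, Chi311, etc) from time of enrollment to completion of therapy or live discharge from the hospital" (similarly Section 5.2: "Change in cytokine levels from time of enrollment to completion of therapy or live discharge from the hospital (whichever comes first"), but it is not tied to the regression. ICU length of stay is not a listed endpoint; days on mechanical ventilation is. Mortality is a separate endpoint, and the ordinal scale in Section 5.2 scores death as 7. Section 15 promises a detailed SAP before the final analysis.

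**The concern.** Length of stay is a poor stand-in for outcome when death can shorten it or prevent it from starting. A patient ventilated for 3 days who dies and one extubated after 3 days both score 3. A patient who moves to comfort care (listed in Section 12.1 as a reason to stop treatment) and dies unventilated scores 0, like a patient who recovers on the ward. A marker that tracks severity well would then be pulled towards no association, or the wrong one, by the patients who matter most to the objective. This holds for a model with a single predictor.

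The open predictor list is a second and lesser matter. Section 9.3 describes "a cytokine panel that will consist of sCD40L, GM-CSF, IFN gamma, IL-2, IL-4, IL-6, IL-8, IL-10, RANTS, TNF-alpha, and VEGF", which is 11 markers, before CCR5 receptor occupancy, Chi3l1 and routine laboratory values are counted. A model of that size in about 16 patients would be close to saturated.

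At stake is the answer to the secondary objective.

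**Working it through.** The plan gives no figure for this analysis, and no alpha, power or effect size, so there is nothing to reproduce. A two-sided 5% level is assumed below.

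**Inputs.** n = 16 (Sections 4.1 and 8.1). Panel of 11 cytokines (Section 9.3). From the lopinavir-ritonavir trial as described in Section 1: 16% ventilated and 15.2% dead by Day 14. Using these rates here is an assumption.

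**Is a death rule likely to be needed?**
- Expected deaths: 16 × 0.152 = 2.4.
- P(at least one) = 1 − 0.848^16 = 0.93. With 5% mortality it is 0.56, and with 20% it is 0.97.
- Expected never ventilated: 16 × 0.84 = 13.4, so most ventilation stays are zero.

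**Model size, if all 11 cytokines entered one model.**
- Residual df = n − 1 − k = 16 − 1 − 11 = 4.
- Mean R² by chance = k/(n − 1) = 11/15 = 0.73.
- R² needed for p < 0.05 = kF/(kF + df), with F(0.95; 11, 4) = 5.94: 65.3/69.3 = 0.94.
- For comparison, k = 3 gives 12 df, mean chance R² 3/15 = 0.20 and critical R² 0.47.

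**Does the overall F test hold its level?** Null simulation, all inputs assumed: 16% ventilated, exponential stays with mean 10 days, zero otherwise. With lognormal markers the test rejects in about 11% of data sets with 3 predictors, and about the same with 11. With normal markers it rejects in about 5%.

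**Cost of omitting a death rule (illustration; all inputs assumed).** One marker, n = 16, correlation 0.7 with latent severity. The most severe patients die and the next most severe are ventilated. Ventilation lasts 1 to 7 days in ventilated deaths and 5 to 19 days in survivors. Linear regression on raw ventilator days is compared with Spearman correlation on ventilator-free days to Day 28 (deaths = 0).

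| Deaths never ventilated | Raw days | Ventilator-free days |
|---|---|---|
| none | 35% | 39% |
| half | 16% | 53% |
| all | 9% | 63% |

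The right-hand column assumes that every death has a marker change. In the middle row, if 25%, 50% or 100% of deaths lack it, 53% falls to about 44%, 32% or 9%.

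**The case against.** The strongest reply is that this is one exploratory analysis in a 16-patient proof-of-concept study, and that Section 15 commits to a detailed SAP before the final analysis. That stands for the missing predictor list and sampling day: on their own they are detail that a SAP can supply. It does not fully answer the death problem. Section 15 presents the SAP as the place for modifications to the described plan, so the length-of-stay regression is the default. It also does not require the SAP to precede sight of the biomarker results.

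A reader might infer that the trial plans a near-saturated model. The documents do not say so. No section states how many predictors enter one model, and the 11-cytokine case is a scenario only.

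A reader might also infer that the trial ignores death. It does not. Mortality at 7, 14 and 28 days is a separate endpoint and the ordinal scale includes death. The gap is confined to the biomarker-outcome regression.

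Finally, the power contrast can be challenged, and rightly. The share of deaths never ventilated, the 0.7 correlation and the assumption that the most severe patients die have no source in the documents. A change score also needs a second sample, which some deaths will lack. A raw-days regression on change scores would lose those patients too; one on Day 0 levels, which Section 15.3 permits, would not.

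**Conclusion.** The concern holds in a limited form. Followed as written, Section 15.3 relates biomarkers to an outcome that does not register death, while the objective names avoidance of death. That mismatch follows from the text and needs no assumption. That deaths will occur is likely (probability 0.93) if the Background mortality applies.

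How much it matters is uncertain. The gain from a death-inclusive outcome is negligible if every death follows ventilation. It can be large if many deaths are unventilated and those patients have a second sample. It is lost if deaths lack that sample. The power figures should not be read as a forecast.

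The predictor question is secondary and conditional on model size. The inflated F test depends on skewed markers, which the documents do not describe. The figure of 16 is approximate, because Section 12.4 allows subjects to be added when research bloods are mishandled. Severity is minor to should-fix.

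**What to change.** In Section 15.3, or in the SAP promised in Section 15, fixed before biomarker results are seen, replace the length-of-stay regression with wording such as:

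> Exploratory. For CCL5, IL-6 and Chi3l1 (if paired samples exist), one marker at a time, the change from Day 0 to Day 7 or live discharge, whichever is earlier, or to the last post-baseline sample if the patient dies before then, will be related to the ordinal score at Day 15 (death = 7; scores 1 and 2 merged) by Spearman correlation with 95% CI. Patients discharged alive are scored 2 or less unless a follow-up call or the hospital record shows readmission or death by Day 15. Patients with no contact on or after Day 15 are treated as missing; scoring them 2 or less is a sensitivity analysis. Where ventilation is the outcome, ventilator-free days to Day 28 (deaths = 0) are used. The Day 0 to Day 3 change is a sensitivity analysis. Patients with no post-baseline sample are listed with their outcome. All correlations (up to nine) are reported with 95% CIs and no significance claim. Other markers, routine laboratory values, ICU stay and raw ventilator days are described only.

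The three markers are those named in the synopsis endpoint. Day 15 is a scheduled in-hospital visit with research bloods (Section 10.10). Merging scores 1 and 2 matches an existing endpoint, "Time to improvement to Score of 2 or less (days", and is needed because the weekly call in Section 10.12 does not list resumption of normal activities.

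**Cost.** Wording only. The bloods, ordinal scores and calls are already planned (Sections 4.1, 10.10 to 10.12, 10.14 and 16.1).

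**Downsides.**
- Fewer markers, and no adjusted model.
- The change window differs between patients and depends partly on outcome.
- Deaths before any second sample are only listed.
- Precision is low. At n = 16, with t = 2.145 on 14 df, |rho| must reach about 2.145/√(2.145² + 14) = 0.50 to exclude zero.
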